**Background and Goals:**

***Dilated Cardiomyopathy***

[figure not shown]
Biventricular heart failure results in chronic passive hepatic congestion. This congestion through a non-inflammatory process will in time result in fibrosis and development of cirrhosis, also known as cardiac cirrhosis. The time for the liver to become impaired and fibrotic is variable, with initial stages of fine fibrosis potentially reversible with improvement of heart function. Unfortunately for some patients by the time they need a heart replacement by transplantation, the liver not only may be at an irreversible stage of cirrhosis but the impaired liver may not have reserve to sustain injury through hypoperfusion at time of transplant and therefore patients need to be evaluated to have a combined liver and heart. This liver evaluation is at present challenging in selecting patients appropriately to have either heart only or combined heart and liver transplantation. Traditional testing and predictors (i.e. MELD score) are often not helpful.

***Fontan-Associated Liver Disease***

Due to advances in medical care and surgical techniques, the population of adults with congenital heart disease (CHD) has been growing exponentially since the 1950s. Survivorship to adulthood is estimated to be greater than 90% of children born with congenital heart disease; with over 1 million adults living in the United States with CHD. One of the more severe forms of CHD is that of functional single ventricle, including hypoplastic left or right heart syndrome, tricuspid or pulmonary atresia. Without palliative surgery, the life expectancy of neonates born with single ventricle physiology is extremely poor with mortality reaching more than 90% within the first year of life. The Fontan procedure, first performed in 1968 as a palliative surgery for tricuspid atresia, has been widely implemented as a staged palliative surgery for single ventricle patients. Although there has been a significant decrease in mortality in the first 25 years post-Fontan, it has been associated with significant cardiac and non-cardiac complications resulting in delayed morbidity and mortality in young adults.

The Fontan procedure allows for passive pulmonary blood flow by creating a direct connection with the inferior and superior vena cava to the lungs. Over time, there is an increase in both pulmonary vascular resistance and ventricular end-diastolic pressure. The pathophysiology of hepatic fibrosis likely shares similarities with typical cardiac hepatopathy with downstream effects causing hepatic venous and sinusoidal congestion resulting in hepatic fibrosis and possible cirrhosis. Hepatic dysfunction has been well documented amongst adults with Fontan physiology with outcomes worsening as a patient is farther out from the surgical intervention (Figure 1).

# Liver in the Fontan

**Figure 1. Hemodynamic relationship of the liver in relation to the Fontan circulation.**

The liver receives approximately 75% of its afferent blood flow from the portal vein which delivers efflux from the mesenteric circulation. The remaining 25% of blood flow to the liver is derived from the hepatic artery. The hepatic vein drains the liver into the IVC which connects into the Fontan circulation.

What is not known is the relative amount of portal vein flow and hepatic artery flow to the liver in the Fontan circulation. It is postulated that the combination of elevated central venous pressure and low cardiac output may compromise portal venous flow such that hepatic artery blood flow increases as a compensatory mechanism of autoregulation. Elevated transhepatic resistance can result in venous-venous collaterals between the portal and hepatic venous systems, decompressing portal hypertension. However, the transhepatic gradient has not been shown to be elevated in the Fontan which could be result of such collaterals or simply reflective of portal hypertension coupled with high downstream hepatic venous pressure.

Evidence over the past few decades has shown that liver injury is universal in the Fontan patient. Over time, the cumulative effects of high central venous pressure/hepatic congestion coupled with relatively lower cardiac output results in liver fibrosis, cirrhosis and even hepatocellular cancer. Hepatic fibrosis appears to be time-related but other risk factors have been identified including elevated systemic venous pressure, decreased cardiac output, decreased heart rate, and older age at initial Fontan operation.

Non-invasive imaging such as computed tomography (CT) and magnetic resonance imaging (MRI) as well as biopsy specimens commonly demonstrate advanced disease. Despite marked morphologic abnormalities, laboratory investigations such as liver function tests are usually minimally affected.] For example, total bilirubin and alkaline phosphatase can be mildly elevated as seen in hepatic congestion but AST and ALT abnormalities are minimal or absent while CT or MRI can show “cardiac cirrhosis.” Simultaneous, transient elastography and MR elastography demonstrate significant abnormalities in liver stiffness, another striking aspect of FALD. This uncoupling of liver function (measured by conventional laboratory means) from liver structure as assessed by imaging and biopsy in FALD continues to be a major area of research. To date, there is no biomarker or test to accurately measure liver function in the Fontan.

Fontan-associated liver disease (FALD) is a poorly understood comorbidity of the Fontan circulation, manifest radiographically and histologically as hepatic congestion, fibrosis, and cirrhosis.[1] Of great concern is a small but growing number of case reports describing hepatocellular cancer in Fontan survivors. Clinically, these marked morphologic findings of fibrosis and cirrhosis are out of proportion to the degree of laboratory markers of hepatic injury and synthetic dysfunction (i.e. conventional liver function tests, albumin, INR) [5]. There is no good predictor of functional liver reserve in patients who will undergo cardiac surgeries such as Fontan revisions or even cardiac transplantation, further underscoring the elusive nature of FALD. The decision to recommend cardiac transplant only or combined heart liver transplant is challenging and requires better tools than currently available.

**Congestive Dilated cardiomyopathy (DCM)** is a condition in which the heart becomes enlarged and cannot pump blood effectively. Symptoms vary from none to feeling tired, leg swelling, and shortness of breath. It may also result in chest pain or fainting. Complications can include heart failure, heart valve disease, or an irregular heartbeat.

The aim of this project is to assess a non-invasive functional liver test in patients with the Fontan circulation or with DCM that may be used for prognostic purposes. Specifically, we aim to determine whether there are alterations in a Methacetin breath test (MBT) in the Fontan or DCM patient and if so, whether it is related to conventional tests of liver and cardiac function. The hypothesis is that the MBT parameters in the Fontan patient is abnormal as a result of alterations in liver perfusion, liver cell metabolic capability and transhepatic resistance secondary to hemodynamics unique to the Fontan as well as end-organ liver damage. Due to lack of robust biomarkers or other risk stratification schemes, we aim to determine whether there is prognostic value in hepatic MBT parameter in the Fontan patient.

**Aims** - The aims of this study are three-fold:

1. To measure MBT parameter in a cohort of patients with Congestive (Dilated) Cardiomyopathy and a group of Fontan patients and compare results to published normal controls.
2. To explore any association between MBT parameter and clinical parameters already available (both baseline values and changes in values after 12 months), including Fontan hemodynamics as assessed by either of the following tests: cardiac catheterization, echocardiography, non-invasive imaging of the liver (CT or MRI), non-invasive assessment of liver stiffness (ARFI, MRE or Fibroscan), laboratory investigations, and clinical characteristics (i.e. age of patient, time since Fontan operation, type of Fontan etc., onset of DCM) . The clinical parameters should be within 3 months of the MBT.
3. To determine whether MBT is predictive of clinical outcomes: heart failure, clinically significant ascites, and time to transplant or death.

**Research Design and Methods** **Study Design:** This is a prospective pilot cohort study in 20 patients with one group of 10 subjects with Dilated Congestive Cardiomyopathy (DCM) and one group of 10 adult subjects with Fontan. All subjects will be recruited from an adult congenital heart disease clinic in a tertiary care center. Patients enrolled in the study will be prospectively followed for 3-5 years and date of liver transplantation as well as survival status will be recorded.

The first Breath Test will be performed after consent is obtained. This first test (visit 1) will be scheduled as close as possible to the day of consent. The MBT test will be repeated one year later (visit 2) provided no contraindications are present.

**Subjects:**

**Inclusion Criteria**

- Written informed consent obtained prior to any study-specific assessments
- Adults patients  $\geq 18$  years of age
- Liver disease secondary to congenital heart disease or cardiomyopathy

**Exclusion Criteria**

- Females of child-bearing potential that are pregnant or breastfeeding
- Participation in other interventional trials
- Pregnant or breastfeeding female
- Allergy to acetaminophen based medications

**Study-Wide Number of Participants:** We anticipate accruing 20 patients from our center.

**Study-Wide Recruitment Methods:** N/A

**Data Collection and Analysis:**

**Predictor variables**

**Congestive cardiomyopathy:**

- Age
- Etiology: *Viral, Alcohol, Amyloid, Unknown* NYHA functional class

*Include all or some of the following tests collected as part of their standard medical care:*

- Six minute walk test
- Cyanosis (saturations  $<90\%$ )
- Ejection fraction or systemic ventricular function (normal, mild, moderate, severe)
- Degree of atrioventricular regurgitation (none, mild, moderate, severe)
- Cardiac index (L/min/m^2), transhepatic gradient, end-diastolic pressure, PVR, SVR
- Cardiac medications (beta-blocker, calcium channel blockers, ACE/ARB, diuretics)
- History of hepatitis, alcoholism, large volume paracentesis, varices, GI bleed, hepatic encephalopathy
- History of heart failure (defined as admission for volume overload)
- Laboratory tests: comprehensive metabolic panel, CBC, PT/INR, NTproBNP, AFP, and troponin T
- Child-Pugh score
- MELD, MELD-Na, and MELD-XI scores
- Abdominal CT or MRI findings consistent with cirrhosis or portal hypertension
- Liver biopsy
- Fibroscan, ARFI or MR Elastography score

**Adult Fontan Associated Liver Disease patients.**

- Age
- Age at Fontan
- Time from Fontan
- Type of Fontan (atrio-pulmonary, lateral tunnel, extracardiac, other)
- History of Fontan revision
- Underlying congenital heart disease lesion
- Systemic right ventricle or left ventricle
- NYHA functional class
- Six minute walk test
- Cyanosis (saturations <90%)
- Ejection fraction or systemic ventricular function (normal, mild, moderate, severe)
- Degree of atrioventricular regurgitation (none, mild, moderate, severe)
- Fontan pressure (mmHg), cardiac index (L/min/m^2), transhepatic gradient, end-diastolic pressure, PVR, SVR
- Cardiac medications (beta-blocker, calcium channel blockers, ACE/ARB, diuretics)
- History of hepatitis, alcoholism, large volume paracentesis, varices, GI bleed, hepatic encephalopathy
- History of heart failure (defined as admission for volume overload)
- Laboratory tests: comprehensive metabolic panel, CBC, PT/INR, NTproBNP, AFP, and troponin T
- Child-Pugh score
- MELD, MELD-Na, and MELD-XI scores
- Abdominal CT or MRI findings consistent with cirrhosis or portal hypertension
- Liver biopsy
- Fibroscan, ARFI or MR Elastography score

Other than the MBT, all testing will be obtained as part of the standard of care evaluation of heart and liver disease in patients with Fontan circulation or DCM.

**Study Timelines:** We anticipate that it will take approximately 2 years to recruit patients who are to be included in this study. Patient will follow 3-5 years.

**Study Endpoints:** The aim of this project is assess a non-invasive functional liver tests in patients with the Fontan circulation or DCM that may be used for prognostic purposes.

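### Both predictor lists name oxygen saturation only as cyanosis below 90%; listing the percentage would keep information that Aim 2 needs, at almost no cost

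*Protocol*

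**What the plan says.** Under Data Collection and Analysis, Predictor variables, the protocol has one list per group. The Fontan list contains "Cyanosis (saturations <90" per cent. The list for congestive cardiomyopathy has the same entry, "Cyanosis (saturations", with the same cut, among items introduced by "Include all or some of the following tests collected as part of their standard medical care". Neither list names the saturation percentage, and no reason is given for the 90% cut.

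Other items in the same lists are kept as quantities. The Fontan list has "Fontan pressure (mmHg), cardiac index" with its unit, and ejection fraction is offered alongside a graded alternative.

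The Aims section sets the use of these variables: "To explore any association between MBT parameter and clinical parameters already available (both baseline values and changes in values after 12 months". The Study Design paragraph gives the size: "one group of 10 subjects with Dilated Congestive Cardiomyopathy (DCM) and one group of 10 adult subjects with Fontan". After the Fontan list the protocol adds: "Other than the MBT, all testing will be obtained as part of the standard of care evaluation of heart and liver disease".

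**The concern.** A cut at 90% cannot be applied without reading a number. If only the category is entered, a saturation of 89% and one of 70% become the same, while 89% and 91% become different.

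The mismatch with Aim 2 is the clearest part, because it needs no assumed prevalence. Aim 2 wants 12-month changes. A fall from 98% to 91%, or from 89% to 75%, counts as no change under the yes/no item, because neither crosses 90%.

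The lists stand under a heading that covers data collection as well as analysis. If the study follows them literally, a later analysis plan cannot recover a percentage that was never entered. With few patients, a cut may also leave zero or one patient on one side, and then the item tells us little or nothing about MBT.

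**Working it through.** **Figure to reproduce.** There is none. The protocol gives no power, significance level, effect size or expected share of cyanotic patients for this item.

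**Inputs from the protocol.** A cut at 90% in both lists; 10 patients per group, 20 in total; associations with baseline values and 12-month changes.

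**Assumptions.** The share *p* of patients below 90% is unknown and is varied. The efficiency formula also assumes a normally distributed predictor linearly related to MBT. The pooled figures assume the same *p* in both groups.

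**Formulas.**
- Relative efficiency of the cut against the continuous value: RE = φ(z_p)² / [p(1 − p)], where φ is the standard normal density and z_p the p-quantile. Information lost = 1 − RE.
- Chance that all *n* patients fall on one side: pⁿ + (1 − p)ⁿ.

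**Worked example, p = 10%.** z = −1.282 and φ = 0.1755, so RE = 0.0308 / 0.09 = 0.342 and the loss is 66%. No variation in 10 patients: 0.9¹⁰ + 0.1¹⁰ = 0.349. In 20 patients: 0.9²⁰ + 0.1²⁰ = 0.122.

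| Assumed share below 90% | RE | Information lost | Effective n out of 10 | No variation, n = 10 | No variation, n = 20 pooled |
|---|---|---|---|---|---|
| 50% | 0.637 | 36% | 6.4 | 0.2% | below 0.1% |
| 30% | 0.576 | 42% | 5.8 | 2.8% | 0.1% |
| 20% | 0.490 | 51% | 4.9 | 10.7% | 1.2% |
| 10% | 0.342 | 66% | 3.4 | 35% | 12% |
| 5% | 0.224 | 78% | 2.2 | 60% | 36% |

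RE is largest at an even split, so 36% is the smallest loss under this model. RE does not contain *n*: the proportional loss is the same at any sample size. The sample size governs only the absolute precision and the chance of no variation.

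In a group of 10, the chance of at most one patient on the smaller side is 38% at p = 20% and 74% at p = 10%.

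**Check by simulation** (20,000 runs, bivariate normal, two-sided 0.05 test of the correlation; the test and the true correlations are assumptions):

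| Setting | Continuous | Cut, p = 50% | p = 30% | p = 20% | p = 10% |
|---|---|---|---|---|---|
| n = 10, correlation 0.7 | about 68% | 43% | 37% | 29% | 19% |
| n = 20, correlation 0.5 | about 64% | 43% | 38% | 33% | 23% |

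**Precision even with the percentage.** At n = 10 and an observed correlation of 0, the Fisher z half-width is 1.96/√7 = 0.741, so the approximate 95% interval is −0.63 to +0.63.

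**The case against.** The strongest case on the other side is that the lists are only lists. The entry may simply define a clinical term. A reader might infer that the protocol fixes a 0/1 coding and throws the reading away, but it says neither. Coding and analysis form are commonly settled in a case report form or analysis plan, which are not shown. In the cardiomyopathy group the item is not even certain to be collected, since that list takes all or some of its tests. This much stands: what can be said is that the percentage is not listed, not that it will be discarded.

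The model can also be challenged. Saturation is capped at 100%. If few patients are below 90%, most values are likely to sit in a narrow band under the ceiling, so normality is least secure where the computed loss is largest. A true threshold at 90% would also change the figures. That stands as a limit on the percentages. It does not favour the cut: the protocol claims no threshold, and a recorded percentage can always be cut at 90% later, whereas the reverse is impossible.

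Finally, Aim 2 does not say that associations are examined within each group of 10. Pooling lowers the risk of no variation, which is why both sets of figures are shown.

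None of this answers the point about 12-month change, which rests on the definition alone.

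**Conclusion.** The point holds as a small, nearly free improvement. Taken as written, both lists yield a yes/no predictor that fits poorly with an aim built on values and changes in values.

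Its size is conditional. Under a normal predictor and a linear relation, the loss is at least 36%, and about 51%, 66% or 78% if 20%, 10% or 5% of patients are below 90%. The chance of no variation at 10% or 5% is about 35% or 60% in a group of 10, and about 12% or 36% in all 20.

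Three stronger readings are tempting and are not supported:
- That a given fraction of the information is lost as a fact. The share below 90% and the shape of the distribution are not in the documents.
- That one group will have no variation. This is likely only if few patients are below 90%; with 30% to 70% below, the chance in a group of 10 is under 3%. The documents do not show which group, if either, would be affected.
- That the percentage would turn this into an informative analysis. It is more efficient, but estimates from 10 or 20 patients stay imprecise.

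Importance is modest. The Fontan list alone has 22 entries, the aim is exploratory, and no conclusion of the pilot rests on this item.

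**What to change.** In both predictor lists, name resting oxygen saturation in percent as the variable. Use it as a continuous or rank variable in the exploratory association analyses with MBT (for example by rank correlation), at baseline and as 12-month change where both readings are available. Keep the below-90% category as a descriptive label.

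The cost is entering a number that has to be read anyway to assign the category. On the protocol's own statement that testing other than MBT is standard of care, no procedure, visit or patient is added. Clinical management is unchanged.

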## PROCEDURES INVOLVED:

### Methods

#### *Screening and consent*

Eligible patients will be screened and recruited through the outpatient Hepatology Clinic, Heart Failure Clinic and the Adult congenital heart disease clinic. They will be approached the day of the scheduled outpatient appointment by the PI or a study coordinator in a private room.

Informed consent will be obtained by the principal investigator, a sub-investigator or a member of the study team who is authorized to give consent. This will allow the potential subject sufficient opportunity to consider whether or not to participate and this will minimize the risk of influence or coercion. The subject will be informed of what the research entails. Any foreseeable risks or discomforts will be discussed with the subject. The protection of confidentiality will be discussed with subjects as well as the subject will be given the name(s)/number(s) of persons to contact should they have any further questions before signing the informed or consent or once they have enrolled in the study. It is reiterated to the subject that participation is voluntary and not participating will not affect present or future medical care. The subject will ask and have

answered any and all questions before signing the informed consent. The subject is given a signed copy of the informed consents(s) and HIPAA authorization(s).

### ***MBT testing***

The C-Methacetin Breath Test (MBT) is a non-invasive test for assessing liver metabolic function. The BreathID® MCS System consists of the BreathID® MCS device and a test kit containing a breath collection cannula and a non-radioactive isotope C-Methacetin solution. It measures and computes the ratio between CO2 and CO2 in the patient's exhaled breath. The components of the MBT system include the

1. MBT BreathID® MCS unit;
2. C-Methacetin solution.

A dedicated flash memory stick for automatic raw data download will be provided to all participating investigative sites.

All components of the MBT system will be provided by Exalenz Bioscience Ltd.

### **The MBT BreathID® MCS Unit**

Exalenz Bioscience Ltd. has developed a molecular correlation spectrometer, based on specific optical-radiation emission and absorption by CO2 and CO2 gases. This device continuously senses exhaled breath and analyzes CO2 in real-time through a breath collection cannula connected to the patient. Based on Molecular Correlation Spectrometry (MCS), the BreathID® MCS device continuously measures CO2 and CO2 concentrations from the patient's breath and establishes the CO2 / CO2 ratio. The cannula continuously transports the breath sample from the patient to the BreathID® MCS device. Results are displayed in real time on the device screen and are printed after the completion of the test. The BreathID® MCS device calculates the delta over baseline (DOB), which can be translated into the percent dose recovery (PDR) and the cumulative percent dose recovery (CPDR) for each time point derived from the ratio difference compared to baseline (normalized/adjusted to the patient's body weight and height as well as substrate dose) throughout the course of the test. The C-Methacetin metabolism begins almost immediately since liquid passes through the stomach to the duodenum, where it is absorbed, without delay. The default breath collection test time is one hour after ingestion of C-Methacetin. The light sources are CO2 and CO2 discharging lamps. By using CO2 and CO2 discharging lamps as light sources, light absorption will be solely due to the existence of CO2 and CO2 in the gas mixtures. Furthermore, by using CO2 and CO2 discharging lamps as light sources, background radiation will be substantially reduced, leading to highly sensitive absorption curves. These highly sensitive absorption curves enable detection of very small variations in CO2 and CO2 concentrations and the CO2 / CO2 ratio. The BreathID® MCS System can detect variations of less than 1/1000 in the CO2 / CO2 ratio measurement. The actual breath collection is automatically done by the device and is not operator dependent. If the patient is not connected properly (e.g. the breath does not reach the device), the BreathID® MCS device will prompt the operator to adjust the nasal cannula. The cannula transports the breath sample from the patient to the BreathID® MCS device. The cannula test kit is a single-use kit and is comprised of a plastic sampling line with an in-line hydrophobic filter (used to reduce the amount of moisture present from the patient's breath) and a Luer-lock connector for connection to the BreathID® MCS device. The device is designed to accommodate an extended range of respiratory rates.
